**NCT number: NCT04431960**

**Document data: September 29, 2023**

## **Study Protocol and Statistical Analysis Plan**

### **1. Purpose/Introduction:**

This study aimed to evaluate the dose-dependent effects of blackcurrant supplementation on bone density in adult women and its relationship to bone metabolism. The feasibility of the pilot clinical study was also assessed. For this purpose, we conducted a pilot double-blind, randomized, placebo-controlled clinical study with blackcurrant supplementation for six months in peri- and early postmenopausal women aged 45–60. The primary endpoint was whole-body BMD. In addition, to delineate the underlying mechanisms of the action, changes in serum markers of bone metabolism following blackcurrant supplementation were also assessed.

## **2. Materials and Methods**

[figure not shown]
### **2.1. Study Participants**

Forty peri- and postmenopausal women aged 45–60 were initially recruited from northeastern Connecticut through newspaper advertisements, flyers, and email. The inclusion criteria for this study were: (1) women aged 45–60 years old; (2) not on HRT for at least one year before the initiation of the study; (3) maintaining normal exercise level (<7 h/week) and willing to avoid exercise 24-h prior to blood and stool sampling and 12-h prior to bone measurements; (4) willing to ingest a dietary blackcurrant supplement or placebo as well as 400 mg calcium and 500 IU vitamin D daily; (5) willing to avoid other dietary supplements for the duration of the study, (6) willing to avoid intake of foods extremely rich in anthocyanins and fermented dairy products, (7) willing to have 3 blood draws and 2 bone scans and (8) willing to take a urine pregnancy test before each bone scan. Exclusion criteria included: (1) those with metabolic bone disease, renal disease, cancer, cardiovascular disease, diabetes mellitus, respiratory disease, gastrointestinal disease, liver disease, or other chronic diseases, (2) heavy smokers (>20 cigarettes/day), (3) perimenopausal women with any chance or plan of pregnancy, (4) taking prescription medications known to alter bone and Ca metabolism; (5) taking anabolic agents; (6) alcohol consumption exceeding 2 drinks/day. Subjects who met the recruitment criteria upon initial phone screening were immediately invited to the study laboratory at the University of Connecticut in Storrs, Storrs, CT, USA.

### **2.2. Study Design**

Upon signing the consent form, an initial physical examination (body weight, height, waist circumference, and blood pressure) was conducted. The participants were also interviewed about their medical history and dietary behaviors by study personnel. Participants had a urine pregnancy test to confirm that they were not pregnant and thus eligible for the bone density measurement using dual-energy X-ray absorptiometry (DXA). All eligible participants completed an additional consent form for the DXA

assessment and scheduled their bone mass measures on or within  $\pm$  3 days of study visit 1 (month 0) and 3 (months 6) at the University of Connecticut Korey Stringer Institute Human Performance Laboratory. Participants were asked to refrain from taking the provided calcium supplements the day before the exam (24 h) to limit potential interference with the DXA measurements.

The participants were taught how to complete 3-day food records (FR) and physical activity records and asked to complete them one week prior to each study visit at months 0, 3, and 6. Subjects who were taking any dietary supplements that are known to affect bone metabolism were asked to stop taking them. After the initial screening visit, subjects underwent a 2-week equilibration period, followed by a 6-month clinical trial period. To avoid potential bone deterioration related to calcium and vitamin D deficiency, all participants took a calcium citrate caplet daily that includes 400 mg calcium and 500 IU vitamin D (Bayer AG, Leverkusen, Germany) beginning 2 weeks before the study and lasting for the duration of the study. After the 2-week equilibration period, study participants were randomly assigned to three groups and asked to consume: (1) one capsule containing 392 mg of blackcurrant powder (low BC group); (2) two capsules containing 392 mg blackcurrant powder per capsule, total 784 mg of blackcurrant powder (high BC group); or (3) one placebo capsule (control group) daily for 6 months. Each 392 mg blackcurrant extract contained 176 mg anthocyanins (min. 40% delphinidin-3-rutinoside, 35% cyanidin-3-rutinoside, 10% delphinidin-3-glucoside and 7% cyanidin-3-glucoside). One capsule was equivalent to about 142 fresh blackcurrants. The blackcurrant powder and composition information was provided by Just the Berries, New Zealand (Just the Berries PD Corporation, Los Angeles, CA, USA). The placebo was

an identical-looking capsule that contained rice powder (supplied by Beehive Botanicals Hayward, WI, USA). The extract and placebo were encapsulated in vegetarian capsules and packaged into coded containers for daily dosing to participants (Beehive Botanicals Hayward, WI). Distribution of the supplements was performed blindly at the study center at month 0 (study visit 1: after the 2-week equilibration period) and month 3 (study visit 2).

Aside from the exclusion of dietary supplements, foods extremely rich in anthocyanins (all berries, grapes, red wine, and berry juices), and fermented dairy products containing viable *Bifidobacteria* or *Lactobacilli*, all participants were instructed to keep their usual dietary habits for the duration of the study. Subjects provided a 12-h fasting blood sample and stool specimen at each study visit at months 0, 3, and 6 for biochemical and metagenome sequencing analysis, and a physical examination (height, weight, waist circumference, blood pressure) was conducted at the initial visit (month 0), month 3, and the end of the treatment period (month 6). This clinical trial was registered at ClinicalTrials.gov (NCT04431960). The proposed project and its procedures were reviewed and approved by the University of Connecticut Institutional Review Board (HR20-0035) prior to the initiation of the project.

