### **3. Statistical Analysis**

Data are reported as mean  $\pm$  standard deviation (SD) unless specified otherwise. Differences with two-sided  $p < 0.05$  were considered significant. Data were analyzed using analysis of variance methods with PROC MIXED in SAS (Version 9.4, SAS Institute, Cary, NC, USA) to determine the main and interaction effects of the two factors, treatment (0, 392, or 784 mg/day blackcurrants), and time (baseline, 3 months, and 6 months). The significance of differences in baseline characteristics was tested by ANOVA or Chi-square/Fisher's Exact test. The significance of changes in all outcome variables was tested by repeated-measures ANOVA with treatment as levels of between-subjects factors and time as levels of within-subjects factors. Percent changes in BMD and bone biomarkers between control and low BC groups and between control and high BC groups were evaluated using *t*-tests.

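### The trial is called double-blind without qualification, but high BC takes two capsules a day against one in the other arms, and no masking of that count is described

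*Combined protocol and SAP*

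**What the plan says.** Section 1 (Purpose/Introduction) of the combined protocol and SAP states: "we conducted a pilot double-blind, randomized, placebo-controlled clinical study". It does not limit the claim to particular arms, or say who was blinded. The same section gives the aim as to "evaluate the dose-dependent effects of blackcurrant supplementation on bone density".

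Section 2.2 (Study Design) sets the daily regimens. Low BC receives "one capsule containing 392 mg of blackcurrant powder (low BC group"). The other two arms are given as "two capsules containing 392 mg blackcurrant powder per capsule, total 784 mg of blackcurrant powder (high BC group); or (3) one placebo capsule".

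Section 2.2 then gives three masking measures. The placebo is "an identical-looking capsule that contained rice powder". Capsules were "packaged into coded containers for daily dosing to participants". Hand-out is covered by "Distribution of the supplements was performed blindly at the study center at month 0", and again at month 3. No filler capsule for control or low BC is mentioned.

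Section 3 (Statistical Analysis) models the "main and interaction effects of the two factors, treatment (0, 392, or 784 mg/day blackcurrants), and time". It adds t-tests of percent change for control against low BC and for control against high BC.

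**The concern.** The blinding claim covers the whole trial, while the procedure described supports it unevenly. A look-alike placebo conceals what a capsule contains. It does not conceal that one arm takes two capsules and the others one, every day for six months.

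The arm that stands out is the one on which the dose question depends most. If some high BC participants recognised their allocation, they might have differed from the rest in adherence, behaviour or willingness to stay. Capsule count and high BC assignment coincide completely, so no re-analysis could separate the effect of the higher dose from the effect of knowing one was on it. A difference seen only at the high dose would then carry less assurance than the same difference seen at the low dose.

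**Working it through.** **Inputs (section 2.2).** Each blackcurrant capsule holds 392 mg. Daily capsules: control 1 placebo, low BC 1 active, high BC 2 active.

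**Step 1: is the two-capsule regimen a misprint?** Daily amount = capsules × 392 mg.
- Control: 0 × 392 = 0 mg
- Low BC: 1 × 392 = 392 mg
- High BC: 2 × 392 = 784 mg

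These reproduce the 784 mg total in section 2.2 and the three treatment levels in section 3. The unequal count is what the plan intends.

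**Step 2: which comparisons have unequal counts?**

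| Comparison | Capsules per day | Planned t-test in section 3? | Revealed by count? |
|---|---|---|---|
| Control vs low BC | 1 vs 1 | Yes | No |
| Control vs high BC | 1 vs 2 | Yes | Yes, to someone who knows the regimens |
| Low BC vs high BC | 1 vs 2 | No | Yes, to someone who knows the regimens |

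One of the two planned t-test contrasts is exposed. The treatment effects in the PROC MIXED model use all three arms, so they include high BC and are exposed too.

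**Step 3: does any stated measure mask the count?**
- *Identical appearance* acts on a single capsule, not on how many are taken.
- *Coded containers* may hide the count from whoever handles them, if the containers were closed and alike. The text does not say. They cannot hide it from the participant who takes the capsules.
- *Blind distribution* concerns the hand-out at months 0 and 3, not daily use between visits.

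**Step 4: what would a participant need in order to infer her arm?** Two things: her own count, which she necessarily has, and the link between counts and arms, which she may not have. With both, two capsules means high BC. One capsule leaves control and low BC undistinguished. Inclusion criterion 4 in section 2.1 speaks only of a supplement or a placebo, without dose levels or counts. The consent pages and the figure that opens section 2 were not available for checking, so the second condition stays open.

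**Step 5: how could this reach the outcomes?** Whole-body BMD by DXA (section 2.4) and serum markers by ELISA (section 2.6) leave little room for expectation to alter a measurement. The remaining route is what participants did: taking the capsules, changing habits, or leaving the study. The documents give nothing from which to compute the size of such an effect.

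**The case against.** The strongest reply is that a count tells a participant nothing unless she knows the regimens, and nothing in the document shows that she did. That stands, and it limits the point to possible unblinding. A reader might infer that high BC participants were in fact unblinded, or that the trial was effectively open-label. The documents do not support either reading.

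A second reply concerns staff. Coded containers and blind distribution may have kept the count from those handing out supplements, performing DXA or running assays. The text neither shows nor excludes this, so the firm statement is about participants; for staff, the description is only incomplete.

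A third reply is that the endpoints are objective and co-interventions were restricted in every arm: common calcium and vitamin D, no other supplements, no foods very rich in anthocyanins, otherwise usual diet, and limited exercise. This also stands. It narrows the route for bias but does not close it, because adherence and dropout are left over.

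Finally, this was a pilot, and the document is written in the past tense, so the conduct of this trial cannot change. That limits the remedy here to reporting. It does not remove the mismatch between the label and the procedure.

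**Conclusion.** The point holds in a limited form. As described, the trial lacks a property that it claims for comparisons involving high BC: daily counts are 1, 1 and 2, and no measure is described that equalises or hides them from the participant. One of the two planned t-test contrasts, the three-arm model and the dose-dependence aim are affected. Control versus low BC is not exposed by capsule count.

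A reader might go further and take masking of control versus low BC as assured. The text supports only that the count does not give that comparison away. Nor can a reader conclude that results at the high dose are biased, or in which direction: the size of any effect on BMD or markers cannot be derived from the documents.

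The conclusion assumes that the regimens were followed as section 2.2 states, and that no count masking was used beyond what is written there. If counts were equalised or otherwise hidden from participants, a sentence saying so would settle the matter for them. The inconsistency in the text is certain; its practical consequence is not. It should be fixed, because the remedy is cheap and the dose question rests on the affected arm.

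**What to change.** **This trial.**
1. Reconcile sections 1 and 2.2: state whether the capsule count was masked, how, and for whom (participants, distributing staff, DXA technician, laboratory).
2. If it was not masked, qualify the double-blind claim for comparisons with high BC, and state that limit beside the high BC and dose-dependence conclusions.
3. Report retention by arm, and adherence by arm if it was recorded. This would not show whether anyone was unblinded, but it lets a reader see whether the likeliest routes for bias differ between arms. Section 1 already names feasibility as an aim, so retention belongs in the report anyway.

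The cost is a few sentences and a short table.

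**Any follow-on trial.** Equalise the daily count with matching placebo capsules, leaving the assigned active amounts unchanged. If these three arms were repeated, two capsules each would mean 0 active + 2 placebo (control), 1 active + 1 placebo (low BC) and 2 active + 0 placebo (high BC), still 0, 392 and 784 mg. The cost is one extra inert capsule a day (2 − 1 = 1) in two of the three arms, a small added burden for those participants.

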### *2.3. Dietary Intake and Physical Activity Assessment*

During the trial, participants were asked to complete 3-day FR and physical activity records at months 0, 3, and 6. The FR data were analyzed using the Nutrition Data System for Research (NDSR, University of Minnesota Nutrition Coordinating Center, Minneapolis, MN, USA). The 3-d FR data included all foods and beverages consumed during two non-consecutive weekdays plus a weekend day of the week following the test visits. The physical activity records were used to estimate the metabolic equivalent of task (MET) scores to confirm participants maintained normal exercise levels (<7 h/week) during the entire intervention period and avoided exercise 24-h prior to study visits.

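### Do the conflicting food-record windows in sections 2.2 and 2.3 leave the trial without a pre-treatment diet baseline?

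*Combined protocol and SAP*

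**What the plan says.** Section 2.2 gives one instruction for both kinds of diary. Participants were shown how to fill in 3-day "food records (FR) and physical activity records and asked to complete them one week prior to each study visit", and the visits are those at months 0, 3 and 6.

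Section 2.3 keeps the same three time points ("participants were asked to complete 3-day FR and physical activity records at months 0, 3, and 6") but then says that the food-record days were "two non-consecutive weekdays plus a weekend day of the week following the test visits". The term test visits is not defined. The same section uses the activity records to confirm, among other things, that women "avoided exercise 24-h prior to study visits".

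The timeline comes from section 2.2: "After the initial screening visit, subjects underwent a 2-week equilibration period, followed by a 6-month clinical trial period". On assignment it says: "After the 2-week equilibration period, study participants were randomly assigned to three groups". Supplements were handed out at month 0 (study visit 1) and month 3 (study visit 2), and month 6 is the end of treatment. No first-capsule date is given. The only other diet information is a single contact around consent, when women were "interviewed about their medical history and dietary behaviors by study personnel".

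Section 3 analyses treatment and time effects on the outcome variables, and percent changes in BMD and bone biomarkers. It mentions a comparison of baseline characteristics without listing them, and it does not mention diet.

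**The concern.** A week before a visit and a week after it are different windows, and at month 0 the treatment start may lie between them. If section 2.3 describes what was done, the month-0 food record would be collected after assignment, possibly with capsules already being taken, and the month-6 record would be collected after treatment had stopped. No woman would then have a food record from before treatment. Month-0 diet could not properly be called baseline, and no change in recorded intake from before to during treatment could be calculated.

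In a supplement trial that asks women to keep their usual diet apart from specified exclusions, the food records are the only repeated evidence that they did so. It is therefore reasonable to ask which window applies.

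**Working it through.** No power or sample-size figure is involved, and the plan gives no figure to reproduce. The check places each record on the trial timeline and then asks which window the rest of the text supports.

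**Placing the records.** With visit day = 0, section 2.2 gives roughly days -7 to -1 and section 2.3 roughly days +1 to +7. Under section 2.2 the month-0 record falls within the 14-day equilibration period, because 7 < 14, and so before randomization. Three readings are possible:

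| Reading | Month 0 | Month 3 | Month 6 | Before / on / after | Pre-to-on changes available |
|---|---|---|---|---|---|
| A. Section 2.2, pre-visit | before | on | on | 1 / 2 / 0 | 2 (0 to 3, 0 to 6) |
| B. Section 2.3, after study visits 1 to 3, capsules started at distribution | on | on | after | 0 / 2 / 1 | 0 |
| C. Section 2.3, month-0 record following the screening visit | before | on | after | 1 / 1 / 1 | 1 (0 to 3) |

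Only reading B removes the pre-treatment record. Compared with A, the treatment period changes for 2 of 3 records per woman under B and for 1 of 3 under C. The month-3 record is on treatment in all three.

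**Is reading C tenable?** It is weak but not excluded. Section 2.2 describes a physical examination at consent and a month-0 examination at what it calls the initial visit, with the same four measures (height, weight, waist, blood pressure). It also places study visit 1 after equilibration. Month 0 is thus used loosely. Against C, section 2.3 ties the records to months 0, 3 and 6 and does not mention screening.

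**Which window does the text favour?**

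1. Section 2.2 gives a single pre-visit instruction covering food and activity records together.
2. Section 2.3 pairs the two diaries at the same time points and uses the activity diary to check the 24 hours before each visit. Only days before a visit can show that.
3. No visit after month 6 is described at which a later diary could be handed in. The nearest contact is a bone scan, allowed up to 3 days after study visit 3. Two non-consecutive weekdays plus a weekend day span at least 4 calendar days (for example Wednesday, Friday, Saturday), so a post-visit diary starting on day +1 could not be complete before day +4.

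These points favour the pre-visit window without proving it. Food diaries could have been handled separately from activity diaries, or returned by a route the text does not describe.

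**What depends on it?** The primary endpoint is whole-body BMD (section 1). Section 3 fits treatment, time and their interaction, and uses *t*-tests for percent changes in BMD and biomarkers. Food-record data enter none of these as an outcome or covariate, so every planned estimate and p-value is the same under A, B and C.

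**The case for a change.** The best case for acting is that the documents alone cannot settle the matter. Section 2.3 is the section that describes the diet data, so a reader may well rely on it rather than on section 2.2. Because section 3 does not list its baseline characteristics, month-0 intake could end up in a baseline table, and under reading B that heading would be wrong. Checking dates is cheap and needs no new data.

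The contradiction stands: both sentences are current text, and neither yields to the other on its face. It is also true that diet should be called baseline only if the record predates treatment. But this is what a careful analyst does with dated diaries in any case, and the plan does not need to direct it. The table heading at risk is one that the documents never say will be produced. Women were also told to keep their usual diet apart from the exclusions, so intake may differ little between adjacent weeks, although the documents give no figure for this.

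**Conclusion.** The inconsistency is real but clerical. At most it alters the label of 2 of 3 food records per woman (reading B). Under the better supported reading, section 2.2 holds, a pre-treatment record exists and nothing is lost. Loss of the diet baseline needs all three conditions together: post-visit collection in practice, test visits meaning study visits 1 to 3, and capsules begun at distribution. The documents establish none of them.

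No planned BMD or biomarker analysis changes under any reading, and no bias is shown. The documents contain no dietary data from which an effect could be calculated. The text is written in the past tense, so the collection window can no longer be altered. What remains is an editorial matter of making the two sentences agree with the dates on the diaries and saying what test visits means. That does not amount to a change in design or analysis. This conclusion rests on section 3 being the full analysis plan, with diet serving only as supporting description.

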### *2.4. Bone Density Assessments*

BMD analyses were conducted at the University of Connecticut Korey Stringer Institute by a licensed radiologic technician at baseline and 6 months using DXA (GE Healthcare Lunar) equipped with appropriate software for whole-body, head, arms, legs, trunk, ribs, spine, and pelvis BMD. Specific positioning and analysis guidelines were followed according to the operator's manual. Calibration, maintenance, and quality control of the equipment were routinely conducted following the maintenance instructions in the manual.

